7.6.10.2 Serum Chemistry

The following will be summarized by treatment group as worst CTC grade on-treatment per subject and as shift table of worst on-treatment CTC grade compared to baseline CTC grade per subject: ALT, AST, alkaline phosphatase (ALP), total bilirubin and creatinine.

The analyses will be conducted using the 30-day safety window.

A by-subject listing of these laboratory parameters will be provided.

7.6.10.3 Electrolytes

The following will be summarized by treatment group as worst CTC grade on-treatment per subject and as shift table of worst on-treatment CTC grade compared to baseline CTC grade per subject: sodium (high and low), potassium (high and low), calcium (high and low), magnesium (high and low), and Glucose Serum (fasting hyperglycemia and hypoglycemia regardless of fasting status).

The analyses will be conducted using the 30-day safety window.

A by-subject listing of these laboratory parameters will be provided.

7.6.10.4 Additional Analyses

In addition, further analyses on specific laboratory parameters will be performed by treatment group:

Abnormal Hepatic Function Test

The number of subjects with the following laboratory abnormalities from on-treatment evaluations will be summarized by treatment group:

- ALT or AST > 3 x ULN, > 5 x ULN, > 10 x ULN and > 20 x ULN
- Total bilirubin > 2 x ULN
- ALP > 1.5 x ULN
- Concurrent (within 1 day) ALT or AST > 3 x ULN and total bilirubin > 1.5 x ULN
- Concurrent (within 30 days) ALT or AST > 3 x ULN and total bilirubin > 1.5 x ULN
- Concurrent (within 1 day) ALT or AST > 3 x ULN and total bilirubin > 2 x ULN
- Concurrent (within 30 days) ALT or AST > 3 x ULN and total bilirubin > 2 x ULN

The analyses will be conducted using the 30-day safety window.

A by-subject listing of these specific abnormalities will be provided.

Abnormal Thyroid Function Test

The number of subjects with the following laboratory abnormalities from on-treatment evaluations will be summarized by treatment group:

- TSH value > ULN and
 - with baseline TSH value \leq ULN
 - with at least one FT3/FT4 test value < LLN within 2-week window after the abnormal TSH test
 - with all FT3/FT4 test values \geq LLN within 2-week window after the abnormal TSH test
 - with FT3/FT4 missing within 2-week window after the abnormal TSH test.
- TSH < LLN and
 - with baseline TSH value \geq LLN
 - with at least one FT3/FT4 test value > ULN within 2-week window after the abnormal TSH test
 - with all FT3/FT4 test values \leq ULN within 2-week window after the abnormal TSH test
 - with FT3/FT4 missing within 2-week window after the abnormal TSH test

The analyses will be conducted using the 30-day safety window.

[figure not shown]
A by-subject listing of these specific abnormalities will be provided.

[figure not shown]
7.6.11 Vital Signs

Vital signs collected on the CRF will be provided in a listing. CG and echocardiogram results will also be listed and summarized by treatment group

7.6.12 Physical Measurements

Physical measurements will be listed by subject.

7.6.14 Pregnancy

A by-subject listing of pregnancy tests results will be provided for randomized female subjects.

[figure not shown]
7.6.15 Adverse Events By Subgroup

[figure not shown]
Overall summary of any AEs and drug-related AEs by worst CTC grade (any grade, grade 3-4, grade 5) presented by SOC/PT and for each treatment group for the following subgroups:

- Sex (Male vs. Female)
- Race
- Age (< 65 vs. 65 - < 75 vs. 75 - < 85 vs. ≥ 85 vs. ≥ 75 vs. ≥ 65)

These analyses will be conducted using the 30-day safety window only.

[figure not shown]

[figure not shown]

[figure not shown]

[figure not shown]
f
s

[figure not shown]

8 CONTENT OF REPORTS

All analyses describe in this SAP will be included in the Clinical Study Report except where otherwise noted. Refer to the Data Presentation Plan for mock-ups of all tables and listings.

9 CONVENTIONS

The following conventions may be used for imputing partial dates for analyses requiring dates:

- For missing and partial adverse event onset dates, imputation will be performed using the Adverse Event Domain Requirements Specification¹⁶
- For missing and partial adverse event resolution dates, imputation will be performed as follows:
 - If only the day of the month is missing, the last day of the month will be used to replace the missing day. If the imputed date is after the death date or the last known alive date, then the latest known alive date or death date is considered as the resolution date.
 - If the day and month are missing or a date is completely missing, it will be considered as missing.
- Missing and partial non-study medication domain dates will be imputed using the derivation algorithm described in 4.1.3 of BMS Non-Study Medication Domain Requirements Specification¹⁷.
- Missing and partial radiotherapy and surgery dates will be imputed using algorithm described in [APPENDIX 2](#).
- For death dates, the following conventions will be used for imputing partial dates:
 - If only the day of the month is missing, the 1st of the month will be used to replace the missing day. The imputed date will be compared to the last known alive date and the maximum will be considered as the death date.
 - If the month or the year is missing, the death date will be imputed as the last known alive date.
 - If the date is completely missing but the reason for death is present, the death date will be imputed as the last known date alive.
- For date of progression after start of study therapy, the following conventions will be used for imputing partial dates:
 - If only the day of the month is missing, the 1st of the month will be used to replace the missing day. In case of the date of death is present and complete, the imputed progression date will be compared to the date of death. The minimum of the imputed progression date and date of death will be considered as the date of progression.
 - If the day and month are missing or a date is completely missing, it will be considered as missing.

- For date of progression to prior therapies, the following conventions will be used for imputing partial dates:
 - If only the day of the month is missing, the 1st of the month will be used to replace the missing day.
 - If the day and month are missing or a date is completely missing, it will be considered as missing.
- For other partial/missing dates, the following conventions were used:
 - If only the day of the month is missing, the 15th of the month will be used to replace the missing day.
 - If both the day and the month are missing, “July 1” will be used to replace the missing information.
 - If a date is completely missing, it will be considered as missing.

The following conversion factors will be used to convert days to months or years:

$$1 \text{ month} = 30.4375 \text{ days and } 1 \text{ year} = 365.25 \text{ days.}$$

Duration (e.g. time-to onset, time-to resolution) will be calculated as follows:

$$\text{Duration} = (\text{Last date} - \text{first date} + 1)$$

Last known alive date will be defined based on all appropriate dates collected on the CRF.

All statistical analyses will be carried out using SAS (Statistical Analysis System software, SAS Institute, North Carolina, USA) unless otherwise noted.

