8.3 Lost to Follow-up

- All reasonable efforts must be made to locate participants to determine and report their ongoing status. This includes follow-up with persons authorized by the participant.
- Lost to follow-up is defined by the inability to reach the participant after a minimum of 3 documented phone calls, faxes, or emails as well as lack of response by participant to 1 registered mail letter. All attempts should be documented in the participant's medical records.
- If it is determined that the participant has died, the site will use permissible local methods to obtain date and cause of death.
- If investigator's use of third-party representative to assist in the follow-up portion of the study has been included in the participant's informed consent, then the investigator may use a Sponsor-retained third-party representative to assist site staff with obtaining the participant's contact information or other public vital status data necessary to complete the follow-up portion of the study.
- The site staff and representative will consult publicly available sources, such as public health registries and databases, in order to obtain updated contact information.
- If after all attempts, the participant remains lost to follow-up, then the last known alive date as determined by the investigator should be reported and documented in the participant's medical records.

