4.1.4 Overall Survival

[figure not shown]
Overall survival (OS) is defined as the time from randomization to the date of death from any cause. For subjects that are alive, their survival time will be censored at the date of last contact date (or “last known alive date”). Overall survival will be censored at the date of randomization for subjects who were randomized but had no follow-up.

[figure not shown]
Survival follow-up will be conducted every 3 months after subject’s off-treatment date.

[figure not shown]

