7.6.1 Deaths

Deaths will be summarized by treatment group. These analyses will be performed on the All Treated LAG-3 Positive Subjects, All Treated LAG-3 Negative Subjects, and All Treated Subjects.

- All deaths, reasons for death
- Deaths within 30 days of last dose received, reasons for death
- Deaths within 100 days of last dose received, reasons for death

A by-subject listing of deaths will be provided for the all enrolled subjects population.

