APPENDIX 2 MISSING AND PARTIAL RADIOTHERAPY AND SURGERY DATES IMPUTATION ALGORITHMS

Procedures – Imputation Rules.

If reported procedure start date is a full valid date then set start date equal to the date part of procedure start date.

In case of partial date use imputation rules described below:

- If only day is missing then
 - If month and year of procedure match month and year of first dose date then impute as date of first dose;
 - If month and year of procedure don't match month and year of first dose date then impute as first day of that month and year.
- If both day and month are missing, then impute as maximum between 01JAN of the year and date of the first dose;
- If date is completely missing or invalid then leave missing.

Note: Imputation is not applicable to data where start date is not collected (for example "PRIOR RADIOTHERAPY" CRF). Set start date to missing in this case.

If reported end date is a full valid date then set end date equal to the date part of the reported end date.

In case of partial date use imputation rules described below:

- If reported end date is partial then set end date equal to the last possible reported end date based on the partial entered reported end date.
- If reported end date is missing, continuing, unknown or invalid then set end date equal to the most recent database extraction date.

If end date was imputed then compare end date to the death date or last known alive date if subject is not dead. If posterior then end date should be imputed to death date (or last known alive date if subject not dead).

Note: Imputation of partial dates only applies to data entered on "RADIOTHERAPY" CRF page. For other CRF pages in case of partial dates set end date to missing.

Surgeries – Imputation Rules.

If reported surgery date is a full valid date then set start date equal to the date part of surgery date.

[figure not shown]
In case of partial date, use one of the two imputation rules described below:

[figure not shown]
A. For data collected on "PRIOR SURGERY RELATED TO CANCER" CRF page:

[figure not shown]
- If only day is missing then impute as the first day of the month;
- If both day and month are missing then then impute as 01JAN of the year;
- If date is completely missing or invalid then leave missing.

B. For data collected on other CRF pages (deemed to be on-treatment/subsequent surgeries):

[figure not shown]
- If only day is missing then

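### A death recorded with a year but no month can be imputed into an earlier calendar year that the record rules out

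*SAP*

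**What the plan says.** SAP section 9 (Conventions) has three rules for incomplete death dates.

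- **Only the day missing:** the first of the month is inserted, and then "The imputed date will be compared to the last known alive date and the maximum will be considered as the death date".
- **Month or year missing:** "If the month or the year is missing, the death date will be imputed as the last known alive date".
- **Whole date missing, reason for death present:** the last known alive date is used.

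The anchor is defined in the same section: "Last known alive date will be defined based on all appropriate dates collected on the CRF". The section opens permissively ("The following conventions may be used for imputing partial dates for analyses requiring dates"), but the death rules themselves are worded as firm instructions.

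The death date feeds several analyses. In SAP 4.1.4, "Overall survival (OS) is defined as the time from randomization to the date of death from any cause". Under SAP 4.1.2 and 4.1.3, a death without earlier progression is an event for DOR and PFS on the date of death. SAP 7.6.1 tabulates "Deaths within 30 days of last dose received, reasons for death" and has a matching 100-day table.

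For the start date of radiotherapy and other procedures, SAP Appendix 2 keeps a known year: "If both day and month are missing, then impute as maximum between 01JAN of the year and date of the first dose". It treats on-treatment and subsequent surgeries the same way.

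**The concern.** The second rule covers a death recorded as, say, 2020 with no month, and nothing in it compares the result with that year. Someone who died in 2020 was alive on 31 December 2019. If the last known alive date is in November 2019, the rule gives a death date that the data exclude. The neighbouring day-missing rule cannot do this, because it respects both the recorded month and the last known alive date.

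The error runs one way. The last known alive date is the earliest that death can have occurred, so the rule never dates a death too late. Where it bites, the event time is shortened and the death moves closer to last dose, possibly into a 30- or 100-day table where it does not belong. Year-only dates are conceivable where contact has been lost, since Protocol 8.3 provides that "The site staff and representative will consult publicly available sources, such as public health registries and databases".

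**Working it through.** The plan states no figure on this point, so there is nothing to reproduce. The check applies the rule literally and compares it with the earliest date the record allows.

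**Worked example (dates invented).** Randomised 1 March 2019, last known alive 15 November 2019, death recorded as 2020. OS in months is (days + 1)/30.4375, using the SAP's conversion and duration formula.

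| Death date used | Days from randomisation | OS (months) |
|---|---|---|
| SAP rule: 15 Nov 2019 | 259 | 260/30.4375 = 8.54 |
| Earliest possible: 1 Jan 2020 | 306 | 307/30.4375 = 10.09 |
| Latest possible: 31 Dec 2020 | 671 | 672/30.4375 = 22.08 |

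The SAP date is between 306 − 259 = 47 and 671 − 259 = 412 days too early.

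- **30-day table.** With last dose on 20 October 2019, the death falls on day 26 under the SAP rule and is counted. The earliest possible day is 73.
- **100-day table.** With last dose on 10 August 2019, the death falls on day 97 and is counted. The earliest possible day is 144.

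Neither case needs a missed visit. Days 26 and 97 lie inside the windows for Follow-up Visit 1 (30 ± 7 days) and Visit 2 (100 ± 7 days), and a death early in January 2020 would precede the next planned contact.

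If the record says 2019 instead, the SAP rule and the corrected rule both give 15 November 2019.

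**How often a year-only death is affected.** Assume that death is uniform over the calendar year and that the gap from last known alive date to death is uniform on 0 to G days, with G no longer than a year. Then:

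- share with the last known alive date in an earlier year = G/(2 × 365.25)
- mean distance of the imputed date before 1 January, in those cases = G/3

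Survival contacts are every 3 months (about 91 days), each with a ± 14-day window.

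| G (days) | Share affected | Mean days before 1 January |
|---|---|---|
| 77 | 77/730.5 = 10.5% | 26 |
| 91 | 91/730.5 = 12.5% | 30 |
| 105 | 105/730.5 = 14.4% | 35 |
| 119 | 119/730.5 = 16.3% | 40 |

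Simulation under the same assumptions gave 10.5%, 12.5%, 14.4% and 16.3%. Longer gaps give larger figures (25% and 60 days at G = 180; 50% and 122 days at G = 365), but these describe prolonged loss of contact, not planned follow-up.

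**What the correction removes.** Averaged over all year-only deaths, it moves the date by 0.125 × 30 ≈ 4 days (G = 91) or 0.144 × 35 ≈ 5 days (G = 105). The mean gap from last known alive date to death is G/2, or 45.5 and 52.5 days. The share of the shortening removed is (G²/(6 × 365.25))/(G/2) = G/1095.75, which is 8% and 10%. At least 90% remains.

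Table misplacement has the same limit. Visits 1 and 2 are centred on days 30 and 100, so about half fall on or before the cut-off. With uniform visit timing, about 54% of year-only deaths that truly occur on days 31–100 between the two visits would be counted within 30 days. About 52% of those after day 100 but before the first survival visit would be counted within 100 days. Most of these arise with no change of calendar year.

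**The case against.** **The conventions are only permissive.** This does not help. No alternative rule is offered, the death rules are firm in their own wording, and no other section overrides them or adds a sensitivity analysis.

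**Year-only deaths will be rare.** This largely stands. Protocol 8.3 also tells sites to obtain the date and cause of death when a death is learned of. It does not suggest that registries yield only a year. Drawing the last known alive date from all suitable CRF dates shortens the gaps.

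**The correction does little for early dating.** This stands, as the working shows. It is a reason to describe the fix modestly, not to keep dates that cannot be true.

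**Appendix 2 is not a true parallel.** Partly right. Its floor is the first dose date, and it concerns procedures and surgeries. Section 9 also drops a known year for progression and adverse-event resolution dates when day and month are missing, but it leaves those dates missing and does not assign one that conflicts with the record. The closer comparison is the SAP's own day-missing rule for deaths.

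**The inferential stakes are low.** This stands. SAP 7.5 calls every analysis other than the primary one descriptive, although 7.5.4 and 7.5.7 name log-rank tests. Under the primary PFS definition, deaths after subsequent anti-cancer therapy are not considered. DOR is censored at subsequent therapy, and a death after progression affects neither endpoint.

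**Conclusion.** The rule is wrong as written for one case: year of death recorded, month missing, last known alive date in an earlier calendar year. There it produces an impossible death date. OS is too short, PFS and DOR are too short where the death is the event, and a death may be misplaced in the 30- or 100-day table. Under planned three-monthly contact and uniform timing, about 12–14% of year-only deaths would be affected, by about 30–35 days on average before 1 January. Both figures rest on those timing assumptions, and the documents do not say how many year-only deaths to expect. Minor severity.

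Three stronger conclusions that a reader might draw are not supported.

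- *Biased treatment comparison.* The same rule applies to both arms, and nothing in the documents shows that partial dates or contact gaps differ between them. ORR, the primary endpoint, is unaffected.
- *False on-treatment deaths.* SAP 7.6.1 has no such category. The tables at risk are those for deaths within 30 and within 100 days of last dose.
- *Every year-only death wrongly dated.* When the last known alive date is in the year of death, the imputed date is early but consistent with the record.

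**What to change.** Replace the month-or-year rule in SAP section 9 with two sentences to this effect: *Where the year of death is recorded but the month is not, use the later of 1 January of that year and the last known alive date. Where the year is not recorded, use the last known alive date.*

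The cost is one change to the SAP text and one line of derivation code, with no new data. The change can only move an impossible date to the earliest possible one. It leaves the date unchanged when the last known alive date already lies in the year of death, so early dating and table misplacement in those cases remain. If more than a few year-only deaths occur, a sensitivity analysis using later admissible dates would show how much they matter.

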10 DOCUMENT HISTORY

Table 10-1: Document History

Version Number	Date	Author	Description
1	06APR2020	[REDACTED]	Original version
2	14JUL2020	[REDACTED]	
-changed PD-L1 CPS stratification factor to consistently have 3 categories throughout document
 
[REDACTED]
 
-Sections 2.1, [REDACTED] and 6.2.1- added information on CPS rescore for certain subjects and the rescore will be the primary value used for those subjects.
 
[REDACTED]
 
-updated wording of PD-L1 in multiple spots to read PD-L1 CPS. Section 8 was switched with section 9 so conventions come at the end of the SAP. -Section 7.2.1 - added analysis for All Randomized LAG-3 Positive Subjects -Section 7.3.2 - added RACE display and REGION display.
 
[REDACTED]
 
-Section 2.1 - changed the wording for the FU and survival visits to take directly from the protocol.
 
[REDACTED]

APPENDIX 1 TIME-TO ONSET AND TIME-TO RESOLUTION DEFINITION AND CONVENTIONS FOR SELECT ADVERSE EVENTS, IMMUNE-MEDIATED ADVERSE EVENTS AND EVENTS OF SPECIAL INTEREST

Time-to onset definition

Time-to onset of AE (any grade) for a specific category is defined as the time between the day of the first dose of study treatment and the onset date of the earliest AE (of any grade) in this category.

The time-to onset of AE (grade 3-5) for a specific category is defined similarly with an onset date corresponding to a grade 3-5 AE.

Time-to onset of drug-related AE (any grade or grade 3-5) for a specific category is defined similarly but restricted to drug-related AE.

Time-to onset for a specific subcategory is defined similarly but restricted to event of this subcategory.

Time-to resolution definition

In order to derive the time-to resolution, overlapping or contiguous AEs within a specific category or subcategory will be collapsed into what will be termed “clustered” AEs. For example, if a subject (without pre-treatment AE) experienced an AE from 1st to 5th January, another AE (with different PT but within same category) from 6th to 11th January and same AE from 10th to 12th January, these will be collapsed into one clustered AE from 1st to 12th January. [Table 10-2](#) is summarizing key derivation steps for each type of clustered AEs.

Time-to resolution of AE (any grade) for a specific category is defined as the longest time from onset to complete resolution or improvement to the grade at baseline among all clustered AEs experienced by the subject in this category per adverse event criteria category. Events which worsened into grade 5 events (death) or have a resolution date equal to the date of death are considered unresolved. If a clustered AE is considered as unresolved, the resolution date will be censored to the last known alive date. Improvement to the grade at baseline implies that all different events in the clustered adverse event should at least have improved to the corresponding (i.e. with same preferred term) baseline grade. This measure is defined only for subjects who experienced at least one AE in the specific category.

The time-to resolution of AE (grade 3-5) for a specific category is defined similarly with an onset date corresponding to a grade 3-5 AE.

Time-to resolution of drug-related AE (any grade or grade 3-5) for a specific category is defined similarly but restricted to drug-related AE.

The time-to resolution of AE (any grade or grade 3-5, drug-related or all) where immune modulating medication was initiated is defined similarly. For data presentation not restricted to IMAE, the additional condition that the subject started an immune modulating medication during the longest AE resolution period will be applied.

Time-to resolution for a specific subcategory is defined similarly but restricted to event of this subcategory.

Table 10-2: Derivation of Clustered AE

Type of clustered AE	Derivation
Any grade	Collapse any on-treatment AE from the same category
Drug-related of any grade	Collapse any on-treatment drug-related AE from the same category
Grade 3-5	Collapse any on-treatment AE from the same category. Resolution will be based on the onset date of the earliest grade 3-5 records (if no grade 3-5 record, clustered AE is excluded)
Drug-related of Grade 3-5	Collapse any on-treatment drug-related AE from the same category Resolution will be based on the onset date of the earliest grade 3-5 record (if no Grade 3-5 record, clustered AE is excluded)

The algorithm for collapsing adverse event records is using the following conventions:

For each subject and specified category, the corresponding adverse event records will be collapsed when:

- 1) Multiple adverse event records have the same onset date.
- 2) The onset date of an event record is either the same day or 1 day later than the resolution date of a preceding event record (contiguous events).
- 3) The onset date of an event record is after the onset date and prior to or on the resolution date of a preceding event record (overlapping events).

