7.6.6.3 Time-to Resolution of Select AE

Time-to resolution of the following specific events will be summarized separately for each category/subcategory.

- Time-to resolution of drug-related select AE (any grade, grade 3-5) by treatment group
- Time-to resolution of drug-related select AE (any grade, grade 3-5) where immune modulating medication was initiated, by treatment group

Time-to resolution analyses are restricted to treated subjects who experienced the specific events. Time-to resolution where immune modulating medication was initiated analyses are restricted to treated subjects who experienced the specific events and who received immune modulating medication during the longest select AE.

The analyses will be conducted using the 30-day safety window.

The following summary statistics will be reported: percentage of subjects with resolution of the longest select AE, median time-to resolution along with 95% CI (derived from Kaplan-Meier estimation) and ranges.

See time-to resolution definition subsection of [APPENDIX 1](#) for additional details.

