7.6.7 Immune-Mediated Adverse Events (US Submission)

IMAEs will be summarized by treatment group for each immune-mediated category / PT using the 100-day safety window:

- Overall summary of non-endocrine IMAEs by worst CTC grade (any grade, grade 3-4, grade 5) where immune modulating medication was initiated presented by Category / PT
- Overall summary of endocrine IMAEs by worst CTC grade (any grade, grade 3-4, grade 5) presented by Category / PT
- Overall summary of non-endocrine IMAEs leading to discontinuation by worst CTC grade (any grade, grade 3-4, grade 5) where immune modulating medication was initiated presented by Category / PT
- Overall summary of endocrine IMAEs leading to discontinuation by worst CTC grade (any grade, grade 3-4, grade 5) presented by Category / PT
- Overall summary of non-endocrine IMAEs leading to dose delay or reduction by worst CTC grade (any grade, grade 3-4, grade 5) where immune modulating medication was initiated presented by Category / PT
- Overall summary of endocrine IMAEs leading to dose delay or reduction by worst CTC grade (any grade, grade 3-4, grade 5) presented by Category / PT
- Summaries of time-to onset and time-to resolution of non-endocrine IMAEs where immune modulating medication was initiated presented by Category
- Summaries of time-to onset and time-to resolution of endocrine IMAEs presented by Category

A by-subject listing of IMAEs will be provided. By-subject listings of time-to resolution for longest IMAEs cluster (any grade and grade 3-5 in separate summaries) will also be provided. For new studies which collect investigator assessment of potential IMAE data, a by-subject listing of AEs considered as immune-mediated events per investigator but not qualified for IMAEs definition will also be provided.

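### Time to resolution uses only the longest cluster per category, so a longer resolved cluster can make a participant count as resolved while another cluster is ongoing or was fatal

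*SAP*

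**What the plan says.** SAP Appendix 1 first merges overlapping or contiguous events of a category into clusters. Episodes further apart stay separate. It then reduces each participant to one value per category: time to resolution "is defined as the longest time from onset to complete resolution or improvement to the grade at baseline among all clustered AEs" the participant had there.

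Two further sentences fix the status and length of unresolved clusters. The first puts fatal clusters, and those whose end falls on the day of death, in the unresolved group. The second sets the length of every cluster in that group: "If a clustered AE is considered as unresolved, the resolution date will be censored to the last known alive date".

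No sentence says what happens when a resolved and an unresolved cluster belong to the same participant, and there is no rule for ties.

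The definition feeds these outputs:

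- SAP 7.6.6.3 reports, for drug-related select AEs of any grade and of Grade 3-5, the "percentage of subjects with resolution of the longest select AE, median time-to resolution along with 95% CI" from Kaplan-Meier estimation.
- The version for events treated with immune-modulating medication is limited to participants "who received immune modulating medication during the longest select AE".
- SAP 7.6.7 summarises time to resolution of IMAEs and adds listings: "By-subject listings of time-to resolution for longest IMAEs cluster (any grade and grade 3-5 in separate summaries) will also be provided".

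**The concern.** A censored length is only a lower bound. If one cluster resolved after 60 days and another was still open after 30, the longest time to resolution is at least 60 days and otherwise unknown. Under Appendix 1 the participant enters as resolved at 60 days. The derivation then does not deliver the quantity that the SAP itself defines.

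The error has one direction within an arm: the percentage resolved can only go up. Short unresolved clusters are the likeliest to lose the comparison. These are rapidly fatal events and events that began shortly before the last known alive date. The SAP deliberately calls fatal clusters unresolved, and the longest-cluster rule can undo that.

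The pattern is foreseeable. Protocol 7.3.6 lets participants resume immunotherapy after drug-related events resolve, and Protocol 7.3.7 provides for Grade 3 events that recur. Protocol 10.3.9 places the ORR analysis at about 24 weeks after the last randomization, when some late events will have little observed length. At stake is how reversible the select AEs appear.

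**Working it through.** **Inputs.** Clustering conventions, longest-cluster rule and censoring rule: SAP Appendix 1. Duration = last date − first date + 1: SAP section 9.

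**Step 1: the SAP's own example.** Events on 1-5, 6-11 and 10-12 January. The second starts one day after the first ends, and the third overlaps the second. The result is one cluster, 1 to 12 January, as the SAP states, lasting 12 − 1 + 1 = 12 days.

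**Step 2: two separate clusters in one category.** Cluster A runs from day 10 to day 69 and resolves: 69 − 10 + 1 = 60 days. Cluster B starts on day 100 and does not resolve.

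| Cluster B | Censored length of B | Result under Appendix 1 | Result if any unresolved cluster makes the participant unresolved, censored at the longest observed length |
|---|---|---|---|
| Fatal, ends day 109 | 109 − 100 + 1 = 10 | Resolved, 60 days | Unresolved, censored at 60 |
| Ongoing, last known alive day 129 | 129 − 100 + 1 = 30 | Resolved, 60 days | Unresolved, censored at 60 |
| Ongoing, last known alive day 189 | 189 − 100 + 1 = 90 | Unresolved, censored at 90 | Unresolved, censored at 90 |

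The misstatement occurs exactly when the longest resolved cluster is longer than every censored one.

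**Step 3: the Grade 3-5 tables.** SAP Table 10-2 excludes a cluster with no Grade 3-5 record. If A is Grade 2 throughout and B is fatal, A drops out and the participant is correctly unresolved. B is hidden there only if A also contains a Grade 3-5 record and is still longer, measured from its first Grade 3-5 record.

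**Step 4: medication-restricted table (select AEs only).** Suppose an untreated cluster lasted 60 days and a cluster treated with immune-modulating medication lasted 30. The longest is the untreated one, so the participant leaves the table meant to describe treated events.

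**Step 5: how large it could be, on assumptions.** The documents give no durations or recurrence rates. Assume exponential lengths with median m1 for the resolved cluster and mc for the censored one. Among participants who have both, the share counted as resolved is m1/(m1 + mc):

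- m1 = 14, mc = 56 days: 14/70 = 20%.
- Equal medians: 50%.
- m1 = 56, mc = 7 days: 56/63 = 89%.

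Simulation with lengths rounded up to whole days gave 20% and 88% at the two ends.

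The overstatement in percentage points is 100 × s × p. Here s is the assumed share of participants in a category with this pattern, and p is the share of those counted as resolved.

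| s | p = 0.33 | p = 0.67 |
|---|---|---|
| 0.05 | 1.7 | 3.4 |
| 0.10 | 3.3 | 6.7 |
| 0.20 | 6.6 | 13.4 |

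These figures show sensitivity. They are not estimates for this trial.

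**The case against.** The case for leaving the text alone has several parts.

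- **The label is honest.** SAP 7.6.6.3 speaks of "percentage of subjects with resolution of the longest select AE" and does not claim that every event resolved. This helps only in part: with a censored competitor it is not known which event is the longest, so the labelled quantity is itself wrong.
- **Deaths are shown elsewhere.** A reader might infer that fatal immune events vanish from the report. They do not. They remain in the Grade 5 columns of SAP 7.6.6.1 and in the death summaries of SAP 7.6.1, and by-subject listings are planned. Those tables do not cover ongoing non-fatal clusters, however, and no visible summary counts participants with any unresolved cluster.
- **The Grade 3-5 tables are largely protected** by Table 10-2, as step 3 shows. This stands.
- **Follow-up reduces the problem.** In survivors the last known alive date keeps moving, so an ongoing cluster gains length and is less easily hidden. This stands, and it is one reason why no single size can be given.
- **The rule is not explicit.** The SAP never says outright that an unresolved cluster competes on its censored length. That is the direct reading of adjacent sentences. If only resolved clusters were compared, more would be hidden. Only an unwritten rule that unresolved counts as longest would prevent it.

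A reader might also infer that the rule favours the experimental arm. The documents give no repeat-event rates by arm, and Protocol 3.3 describes the combination's safety profile as similar to that of nivolumab alone. No between-arm direction follows.

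**Conclusion.** The point holds as a derivation error of limited reach. It affects only participants with two or more separate clusters in a category, and among them only those whose longest resolved cluster exceeds the censored length of every unresolved one. The percentage with resolution is then overstated, mainly in the any-grade select-AE tables.

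The IMAE summaries and listings inherit the Appendix 1 definition, so the same misclassification can occur there. SAP 7.6.7 does not name a percentage resolved, though, so that statistic should be criticised for select AEs only. The medication-selection gap is likewise confined to select AEs, because Appendix 1 applies the condition only to presentations not restricted to IMAEs.

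The size is unknown. The range of 1.7 to 13.4 percentage points rests entirely on assumed pattern shares of 5% to 20% and assumed masking of 33% to 67%. A material distortion of the Kaplan-Meier median is a tempting inference but is not established. Under the fix below the recorded times stay the same and some events become censored, so the median can only stay or lengthen, by an amount the documents do not determine. These are descriptive safety summaries, and the primary endpoint is untouched.

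**What to change.** In SAP Appendix 1, add three things.

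1. If any cluster in the category is unresolved or Grade 5, the participant is counted as unresolved and censored at the longest observed cluster length, whether completed or censored. Otherwise the longest resolved cluster is used, as now. This handles several unresolved clusters, makes ties immaterial and avoids early censoring at the length of a short fatal cluster.
2. For the select-AE immune-modulating-medication version only, choose the longest among clusters in which the medication was started.
3. In the summaries, add a row with the number of participants who have any unresolved or Grade 5 cluster in the category.

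The cost is a wording change and a derivation change on data already collected. Resolution percentages will be slightly lower and will differ from the sponsor's standard table.
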